### 9.1.3. Dose Modifications and Delays for Toxicity Related to Study Drug

Patients who develop  $\geq$  Grade 3 adverse event(s) considered by the investigator to be related to study drug (with the exceptions noted below) will have study treatment interrupted until all drug-related toxicities have resolved to  $\leq$  Grade 1. Once these toxicities have resolved to  $\leq$  Grade 1, the patient may resume study treatment at a reduced dose of 250 mg/day. No more than one dose reduction is permitted. Patients who require more than one dose reduction will have study drug discontinued and enter the Follow-up Period.

The exceptions are:

- asymptomatic Grade 3 elevations of amylase or lipase,
- Grade 3 elevation of alkaline phosphatase in a patient known to have bone metastases,
- Grade 3 elevation of glucose in a patient receiving systemic corticosteroids,
- Grade 3 creatine phosphokinase [CPK] elevation in the absence of muscle symptoms,
- Grade 3 sodium values  $\geq 126 \text{ mmol/L}$  in a patient with diarrhea)

Patients for whom toxicity persists beyond 21 days despite dose interruption may resume study treatment at a reduced dose of 250 mg/day only with permission from the responsible Medical Monitor.

If study treatment is withheld, the patient should be instructed not to make up the withheld doses.

T٤	ıb	le	5	:

ed AEs

Occurrence	Grade 1	Grade 2	Grade 3	Grade 4
First appearance	
 
No action with study drug
 
For diarrhea start loperamide, monitor for dehydration
 
For rash start topical steroids (see Section 9.1.4.2)
 
For QTc prolongation no action
 
	
 
No action with study drug
 
For diarrhea start/increase loperamide, monitor for dehydration
 
For rash topical steroids ± doxycycline (see Section 9.1.4.2)
 
For QTc check con-meds and electrolytes, correct as indicated
 
For confirmed pneumonitis interrupt and consult Medical Monitor
 
	
 
Interrupt treatment until resolved to Grade 0-1. If interruption < 21 days restart at 250 mg/day. If interruption ≥ 21 days, check with Medical Monitor.
 
In addition, for QTc check con- meds, electrolytes and consult Medical Monitor (see Section 9.1.4.3.1 for restarting and monitoring instructions).
 
For creatinine in absence of renal dysfunction no interruption.
 
	Discontinue. Consult Medical Monitor if continuation is in patient's best interest. In addition, for QTc hospitalize patient and perform cardiology evaluation (see Section 9.1.4.3.1)
appearance			drug	drug

# 9.1.3.1. Requirements for Continuation of Treatment Post Cycle 1

Patients must fulfill the following criteria in order to commence a new cycle of treatment:

- all related  $\geq$  Grade 3 AEs have resolved to  $\leq$  Grade 1
- serum potassium and magnesium above the lower limit of normal
- no arrhythmias, pathologic bradycardia, or associated symptomology
- $QTcF \le 470$  msec and increase from baseline  $\le 60$  msec unless Medical Monitor has given permission to continue
- no concurrent medications that prolong QTc (see Appendix 4)
- no evidence of progressive disease
- no additional therapeutic interventions for glioblastoma
- no strong inhibitors or inducers of CYP3A4, CYP2C8, CYP2D6 or CYP1A2 (see Appendix 4)

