Patients who develop $\geq$ Grade 3 adverse event considered by the investigator to be related to study drug (with the exception of asymptomatic Grade 3 elevations of amylase or lipase, Grade 3 elevation of glucose in a patient receiving systemic corticosteroids, Grade 3 creatine phosphokinase [CPK] elevation in the absence of muscle symptoms, or Grade 3 sodium values $\geq$ 126 mmol/L in a patient with diarrhea) will have study treatment interrupted until the $\geq$ Grade 3 drug-related toxicities have resolved to $\leq$ Grade 1 (refer to Section 9.1.3).
Once toxicities have resolved to $\leq$ Grade 1, the patient may resume study treatment at a reduced dose of 250 mg/day. No more than one dose reduction is permitted. Patients who require more than one dose reduction will have study drug discontinued and enter the Follow-up Period.
Patients for whom toxicity persists beyond 21 days despite dose interruption may resume study treatment only with permission from the responsible Medical Monitor.
If study treatment is withheld, the patient should be instructed not to make up the withheld doses.
Study treatment will continue until disease progression, unacceptable toxicity, patient or physician decision to discontinue, or death. Assessments for disease response will occur at week 4 and 8 and then every 8 weeks using the RANO criteria (see Appendix 2).
Upon treatment discontinuation, patients will be followed every 8 weeks for survival.
Tumor samples will be used for exploratory biomarker research including, but not limited to, evaluation of EGFRvIII expression by immunohistochemistry (IHC) or real-time Polymerase Chain Reaction (PCR). An appropriate histopathological definition and cutoff for EGFRvIII pos tumors will be established, and outcome in this subpopulation will be evaluated in addition to the overall study population.
To characterize the safety and tolerability profile of tesevatinib, patients will be monitored throughout the study for adverse events (all grades), serious adverse events, and any adverse events requiring drug interruption or discontinuation. Patients will undergo safety evaluations, including physical examination (PE), vital sign measurements, hematology, serum chemistry, urinalysis and electrocardiogram (ECG).

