# 7. INVESTIGATIONAL PLAN

# 7.1. Overview of Study Design

This is a multicenter, Phase 2 study to assess the activity of tesevatinib in patients (n = 40) with recurrent glioblastoma. This study will be conducted at up to 10 sites in the United States.

The availability of paraffin-embedded tumor sample diagnostic of glioblastoma is mandatory for entry into the study. Tumor samples will be evaluated for the EGFRvIII mutation and for EGFR gene amplification. Tissue from recurrent surgery is preferred, but tissue from initial surgery is sufficient for study entry. Baseline MRI is mandatory.

After completion of the screening assessments and confirmation of study eligibility by the Medical Monitor upon review of an inclusion package, tesevatinib will be orally administered to all patients at a dose of 300 mg once daily. A cycle will be considered as 28 days. Patients will be evaluated for efficacy according to the RANO criteria.

Patients who develop  $\geq$  Grade 3 adverse event(s) considered by the investigator to be related to study drug (with the exceptions noted in Section 9.1.3) will have study treatment interrupted until the drug-related toxicities have resolved to  $\leq$  Grade 1. Once toxicities have resolved to  $\leq$  Grade 1, the patient may resume study treatment at a reduced dose of 250 mg/day. No more than one dose reduction is permitted. Patients who require more than one dose reduction will have study drug discontinued and enter the Follow-up Period.

Patients for whom toxicity persists beyond 21 days despite dose interruption may resume study treatment only with permission from the responsible Medical Monitor.

If study treatment is withheld, the patient should be instructed not to make up the withheld doses. Section 9.1.3 provides detailed instructions concerning dose interruptions and reductions.

Study treatment will continue until disease progression, unacceptable toxicity, patient or physician decision to discontinue, or death. Assessments for disease response will occur at week 4 and week 8 and then every 8 weeks thereafter using the RANO criteria (Appendix 2).

Upon treatment discontinuation, patients will be followed every 8 weeks for survival.

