### 9.1.4.4. Elevated Serum Creatinine

Patients with increases in serum creatinine to  $> 2 \times ULN$  should be evaluated for non-renal causes of renal dysfunction, such as dehydration due to diarrhea. Cystatin C values should also be utilized to evaluate renal function. Dose interruptions and reductions are not necessary in the absence of renal dysfunction.

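### The new-cycle criterion in Protocol 9.1.3.1 carries no exceptions, so read literally it withholds drug for five Grade 3 event types that the protocol elsewhere says need no interruption

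*Protocol*

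**What the plan says.** **General rule (Protocol 9.1.3).** Patients with a related adverse event of Grade 3 or higher ("with the exceptions noted below) will have study treatment interrupted until all drug-related toxicities have resolved to" Grade 1 or lower. They may then resume at 250 mg/day, and only one reduction is allowed. Five exceptions are itemised: asymptomatic amylase or lipase, alkaline phosphatase with known bone metastases, glucose on systemic corticosteroids, CPK without muscle symptoms, and sodium of at least 126 mmol/L with diarrhea. Creatinine is not among them.

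**Creatinine.** The Grade 3 cell of Table 5, inside 9.1.3, says: "For creatinine in absence of renal dysfunction no interruption". Section 9.1.4.4 says: "Dose interruptions and reductions are not necessary in the absence of renal dysfunction".

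**New-cycle rule (9.1.3.1).** The lead-in is mandatory: "Patients must fulfill the following criteria in order to commence a new cycle of treatment". Eight criteria follow. The first covers all related events of Grade 3 or higher ("Grade 3 AEs have resolved to" Grade 1 or lower) and names no exception. Only the QTcF criterion has a release: "unless Medical Monitor has given permission to continue".

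**Other places.** The synopsis gives a four-item list beginning "with the exception of asymptomatic Grade 3 elevations of amylase or lipase, Grade 3 elevation of glucose in a patient receiving systemic corticosteroids"; it lacks creatinine and alkaline phosphatase and refers the reader to 9.1.3. Section 7.1 simply points there ("with the exceptions noted in Section 9.1.3").

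**The concern.** The protocol decides that certain Grade 3 laboratory rises should not stop treatment, then applies a rule at every cycle start that takes no account of that decision. A site that follows Table 5 and keeps a patient on drug must, on the words of 9.1.3.1, withhold drug at the next Day 1 if the value is still above Grade 1.

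Creatinine is the case that matters most, because the protocol expects it. Section 5.2 reports rises up to Grade 3 without other signs of renal failure, with unchanged cystatin-C, and attributes them to MATE transporter inhibition. It is also a named event of special interest in 9.1.4.

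At stake is consistent dosing: two sites could treat the same patient differently depending on which part of 9.1.3 they apply. The differences would then enter the SAP's tabulations of exposure and dose alterations (SAP 3.7) and of events leading to dose modification or discontinuation (SAP 3.10.1).

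**Working it through.** The plan gives no figure to reproduce here. The check sets the rules side by side.

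**Step 1. Each exemption against the first criterion of 9.1.3.1.** The last column assumes that the event is related, was Grade 3, and is still above Grade 1 on Day 1.

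| Grade 3 event | Where exempted | Can it be Grade 3 in this study? | New cycle under 9.1.3.1 |
|---|---|---|---|
| Creatinine, no renal dysfunction | Table 5; 9.1.4.4 | Yes; seen up to Grade 3 (5.2) | Blocked |
| Amylase or lipase, asymptomatic | 9.1.3; synopsis; 9.1.4.5 for amylase | Yes | Blocked |
| Alkaline phosphatase, bone metastases | 9.1.3 | Yes, though an unlikely setting in glioblastoma | Blocked |
| Glucose on corticosteroids | 9.1.3; synopsis | Yes | Blocked |
| CPK, no muscle symptoms | 9.1.3; synopsis | Yes | Blocked |
| Sodium of at least 126 mmol/L with diarrhea | 9.1.3; synopsis | No: 11.3.9 makes 126–130 Grade 2 and 120–125 Grade 3 | Not caught |

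Count: 5 itemised + 1 creatinine − 1 sodium = 5 event types.

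**Step 2. How often the criterion applies.** Week 24 is 24 × 7 = 168 days = 6 × 28, so Cycle 7 Day 1 is Day 169. The criterion is therefore applied at the start of Cycles 2 to 6, which is 5 occasions before the primary endpoint time. This counts opportunities, not harm.

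**Step 3. One patient traced through the rules.** Take a related Grade 3 creatinine rise without renal dysfunction.

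- Table 5 and 9.1.4.4: continue, with no hold and no reduction.
- 9.1.3.1 at the next Day 1: do not start the cycle until Grade 1 or lower. It says nothing about dose on restarting.
- The itemised 9.1.3 list read alone: hold, then resume at 250 mg/day, using 1 of 1 permitted reductions. A later toxicity that needs a reduction would then mean discontinuation.

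**Step 4. Dose consequence of the list-only reading.** Full dose: 300 × 28 = 8,400 mg per cycle. Reduced dose: 250 × 28 = 7,000 mg per cycle. Difference: 1,400 / 8,400 = 16.7%. This follows only from the third reading in Step 3, not from 9.1.3.1.

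**The case against.** The strongest reply is that 9.1.3 largely resolves the creatinine question itself. Its lead-in promises exceptions further down, Table 5 lies further down in the same section, and 9.1.4.4 is devoted to this event. Two specific instructions should outweigh a list that is silent. The synopsis sentence refers to 9.1.3 and is visibly a shortened version, so it is not an independent contradicting rule. All of this stands, and it makes the missing list entry a secondary defect. It does not reach 9.1.3.1, which comes after Table 5, does not refer to it, and also blocks events that are on the list.

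A second reply is that 9.1.3 lets a patient whose toxicity lasts beyond 21 days resume with the Medical Monitor's permission. That is a real way out, but it presupposes an interruption and restarts at 250 mg/day. It does not keep an exempt patient on uninterrupted full dose.

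A third is that an isolated laboratory value is an adverse event only if clinically significant (11.3.9), so some rises never trigger either rule. This stands in part. However, 12.1.6 counts a need for additional monitoring as clinically significant, and 9.1.4.4 asks for evaluation above 2 × ULN. Amylase and CPK are laboratory values too, yet the sponsor still listed them.

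A reader might infer that each such creatinine rise costs the patient 16.7% of dose and the only reduction. The documents do not support that: it requires a site to overlook both Table 5 and 9.1.4.4. A reader might also count six blocked event types; the sodium grading in 11.3.9 removes one.

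**Conclusion.** The point holds, and its core is the first criterion of 9.1.3.1. Read literally, that criterion blocks the next cycle for five Grade 3 event types that the protocol exempts from interruption. The omission of creatinine from the itemised 9.1.3 list and the synopsis is a lesser, related inconsistency.

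This rests on three assumptions: the event is recorded as a related adverse event, it is still above Grade 1 on a Day 1, and the site applies 9.1.3.1 as written. The documents state no precedence between the parts of 9.1.3.

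Severity is minor to moderate. The documents give no frequency, onset time or hold length for these events, so neither the number of patients affected nor a cumulative dose effect can be estimated. Nothing here changes sample size, power or the primary analysis. No conflict is claimed at Grade 4.

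**What to change.** 1. In 9.1.3.1, add to the first criterion: *except events exempted from interruption in 9.1.3, Table 5 or 9.1.4*. This is the essential change; without it, correcting the lists would still leave dosing blocked at the next Day 1.
2. In the 9.1.3 list and, for consistency, the synopsis, add: *Grade 3 creatinine elevation without renal dysfunction (assessed with cystatin-C)*. Section 7.1 only points to 9.1.3 and needs no edit.

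The cost is one clause and one item in two lists, carried in a protocol amendment with IRB submission and approval (Section 16). It needs no extra patients or visits. Cystatin-C is already in the Day 1 panel through Cycle 24. It is not required in the Day 15 chemistry of Cycles 2 to 6 or in the panel after 24 cycles; there, a site would rely on the existing direction in 9.1.4.4 to use it.

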### 9.1.3.2. Study Drug Discontinuation

Withdrawal of a patient from study treatment means that no further tesevatinib is administered but the remaining study visits or procedures are performed and follow-up data are collected.

A patient's study drug may be prematurely discontinued for any of the following reasons:

- Progression of disease
- An AE requires permanent discontinuation of study drug
- Voluntary withdrawal by patient
- Protocol deviation
- Patient lost to follow-up
- Patient death
- Termination of study by sponsor

Patients that have study drug discontinued due to toxicity are to be followed until there is either:

- Resolution or stabilization to baseline or Grade 1
- The patient is lost to follow-up
- The event is otherwise explained

### 9.1.4. Management of Adverse Events of Special Interest

AEs of special interest include the following: diarrhea, skin rash, QTc(F) prolongation, elevated serum creatinine, elevated serum amylase and ILD. Unless otherwise specified, study drug may be held for up to 21 days at the discretion of the investigator.

### 9.1.4.1. Diarrhea

Diarrhea should be managed with loperamide. On first occurrence of Grade 1 diarrhea initiate loperamide and monitor patient's electrolytes and hydration status. Patients with severe diarrhea who are unresponsive to loperamide or other anti-diarrheals or who become dehydrated require interruption of study drug until resolution to  $\leq$  Grade 1 in severity. If Grade 4 diarrhea occurs, the Medical Monitor should be consulted about study drug decreases or discontinuation. In the event of severe or persistent diarrhea, nausea, anorexia, or vomiting associated with dehydration, study drug should be interrupted, and appropriate measures should be taken to rehydrate the patient intensively via intravenous fluid administration. In addition, renal function and serum electrolytes, including potassium and magnesium, should be monitored in patients at risk of dehydration.

### 9.1.4.2. Skin Rash

Skin rash should be managed according to locally accepted clinical recommendations. Study drug may be held up to 21 days for Grade 3 rash.

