## 5.2. Safety Profile of Tesevatinib

Tesevatinib has been evaluated in 6 clinical studies in various solid tumors in more than 275 patients, of whom at least 50 received the recommended dose of 300 mg daily. The safety profile is similar to that of other agents in this class, with predominantly GI and skin AEs. The most frequently reported AEs associated with tesevatinib use are diarrhea, skin rash, fatigue, nausea, cough, dyspnea, dry skin, vomiting, constipation, vomiting, anorexia and QTc prolongation (see

Investigators Brochure for further detail). The AEs of special interest are as follows (refer to Section 9.1.4 for instruction on management of these AEs):

**Diarrhea:** Diarrhea is an expected AE for agents like tesevatinib that have significant EGFR inhibitor activity. Grade 3 diarrhea was the dose-limiting toxicity. At doses below those that cause dose-limiting toxicity, diarrhea has been effectively managed by starting loperamide upon occurrence of grade 1.

**QTc Prolongation**: In clinical trials of tesevatinib, cases of QTc prolongation have been observed.

In patients with malignancies treated in the clinical program at  $\geq$  300 mg daily or 350 mg intermittently, the majority of whom had advanced metastatic NSCLC, approximately 20% were found to have QTc prolongation based on machine read ECGs at some time during treatment that met the CTCAE v3 definition of an AE. The majority of these were Grade 2 and 3 with no Grade 4. There were no clinical findings associated with the ECG changes.

No SAEs of syncope, convulsions, sudden death, ventricular tachycardia, fibrillation, flutter, or torsades de pointes have been received for the > 275 patients exposed to tesevatinib.

PK data from the clinical program demonstrated that QTc prolongation increased with increasing tesevatinib plasma concentration which correlated with dose administered.

Patients in this study will be monitored carefully for QTc prolongation, and a central laboratory will review all ECGs.

**Skin Rash:** Acneiform skin rash is an expected adverse event for agents like tesevatinib that have significant EGFR inhibitor activity. The rash characteristically involves the chest and face. Paronychial involvement, although characteristic of EGFR inhibitors, has not been seen in tesevatinib studies.

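### For drug-related Grade 3 rash, Section 9.1.4.2 makes the hold optional and contemplates restarting at the same dose, while Section 9.1.3 and Table 5 require interruption and a 250 mg/day restart

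*Protocol*

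**What the plan says.** **General rule.** Section 9.1.3 covers events of Grade 3 or higher that the investigator judges drug-related. These patients "will have study treatment interrupted until all drug-related toxicities have resolved to" Grade 1 or lower. Section 7.1 uses nearly the same words ("will have study treatment interrupted until the drug-related toxicities have resolved to" that level), and the synopsis agrees. After resolution, in the synopsis wording, "the patient may resume study treatment at a reduced dose of 250 mg/day". If toxicity lasts beyond 21 days, 9.1.3 allows 250 mg/day only with the Medical Monitor's permission. Only one reduction is allowed: "Patients who require more than one dose reduction will have study drug discontinued and enter the Follow-up Period".

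**Table 5, Grade 3 cell, first appearance.** "Interrupt treatment until resolved to Grade 0-1". Restart is at 250 mg/day if the interruption is shorter than 21 days; otherwise the site checks with the Medical Monitor.

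**Rash.** Section 9.1.4.2 says: "Study drug may be held up to 21 days for Grade 3 rash". Under its suggestions for a rash that reappears, it refers to unacceptable rash recurring once tesevatinib has been reintroduced at an unchanged dose, and says reduction should then be discussed with the Medical Monitor. No grade is named there, and nothing in 9.1.4.2 points to 9.1.3 or Table 5.

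**Which section to follow.** Section 7.1 states that "Section 9.1.3 provides detailed instructions concerning dose interruptions and reductions". Section 5.2, however, sends readers to 9.1.4 for managing the events of special interest, which include rash.

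**The concern.** Two parts of the protocol give different dosing instructions for the same event. One requires the drug to be stopped and the dose lowered on restart. The other makes stopping a choice and, a little later, treats a same-dose restart as ordinary. Section 5.2 says that "Acneiform skin rash is an expected adverse event for agents like tesevatinib", so sites should expect to consult the rash text.

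What is at stake is how patients are dosed. Two sites could handle the same related Grade 3 rash differently, one lowering the dose and the other not. Because only one reduction is permitted, the choice also affects what happens at that patient's next toxicity.

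**Working it through.** The plan states no figure to reproduce. The check sets the texts side by side and then follows one patient through each.

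**1. Is the hold mandatory?** In 9.1.3, 7.1, the synopsis and the Table 5 Grade 3 cell: yes, for a drug-related event. In 9.1.4.2: worded as optional, with no causality limit. The opening of 9.1.4 also leaves holds of up to 21 days to the investigator unless otherwise specified.

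**2. Is rash exempt from the general rule?** The 9.1.3 exceptions are amylase or lipase, alkaline phosphatase with bone metastases, glucose on corticosteroids, CPK without muscle symptoms, and sodium with diarrhea. The synopsis lists four of these five, without alkaline phosphatase. The Table 5 Grade 3 cell adds creatinine without renal dysfunction. Rash appears in none of the three.

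**3. What is the restart dose?** In 9.1.3 it is 250 mg/day, both after resolution and, with permission, beyond 21 days. Table 5 names 250 mg/day for interruptions under 21 days and no dose for longer ones. The synopsis and 7.1 also name no dose beyond 21 days. Section 9.1.4.2 prescribes no dose, but its closing sentence presupposes the same dose.

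**4. Do the cross-references settle it?** Only in one direction. The Table 5 Grade 1 and Grade 2 cells send the reader to 9.1.4.2 for rash treatment. Section 9.1.4.2 does not send the reader back, and its Grade 3 treatment list (dermatology referral, topical steroids, doxycycline, oral steroids) does not mention interruption.

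**5. One patient on 300 mg/day with a related Grade 3 rash:**
- Under 9.1.3: interrupt, wait for Grade 1 or lower, resume at 250 mg/day. The one reduction is used, so the next toxicity that needs a reduction ends treatment.
- Under 9.1.4.2 read alone: either continue at 300 mg/day, or hold and restart at 300 mg/day. The reduction is unused, so the next such toxicity leads to 250 mg/day.

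Difference in restart dose: (300 − 250) / 300 = 16.7%, or 50 mg × 28 days = 1,400 mg per cycle.

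**6. What limits the divergence?** Section 9.1.3.1 bars a new cycle until related events of Grade 3 or higher have fallen to Grade 1 or lower. Continued dosing is therefore confined to the current cycle. That criterion sets no restart dose.

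**7. Is rash alone in this?** No. Section 9.1.4.1 requires interruption only for severe diarrhea that does not respond to treatment or causes dehydration, and for severe or persistent GI symptoms with dehydration. It gives no restart dose and no pointer to 9.1.3. A related Grade 3 diarrhea that responds to loperamide without dehydration must be interrupted under 9.1.3, but nothing in 9.1.4.1 says so.

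**The case against.** The best defence is that the documents already show which rule governs. Section 7.1 names 9.1.3 as the place for interruption and reduction instructions, and the synopsis refers to it too. The Table 5 Grade 3 cell has special lines for QTc and creatinine but none for rash, so rash takes the default. The sentence in 9.1.4.2 can be read as a ceiling on the length of a hold, since 21 days is the threshold used elsewhere. The same-dose sentence sits among suggestions, names no grade, and fits a discretionary hold for a milder rash under the opening of 9.1.4. Section 11.5 adds regular medical review that pays attention to rash management.

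Most of this stands, and it makes 9.1.3 the probable governing rule. It does not remove the conflict. A ceiling on duration does not turn an optional hold into a required one. The same-dose sentence is not limited to milder or unrelated rash. Section 5.2 directs sites to 9.1.4 with no route back from 9.1.4.2, and Section 11.5 sets no dosing rule.

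A reader might also infer that rash is the only special-interest event with this gap. The diarrhea subsection shows otherwise. Nor can the number of extra 300 mg doses be counted: that would need an onset time for Grade 3 rash, and 9.1.4.2 gives only the usual timing and peak of acneiform rash in general.

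**Conclusion.** The inconsistency is real but minor. For drug-related Grade 3 rash, 9.1.4.2 words the hold as optional and contemplates a same-dose restart, against a mandatory interruption and a 250 mg/day restart elsewhere. The possible consequences are continued dosing within the current cycle, a restart dose of 300 rather than 250 mg/day, and a different count of reductions used.

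This rests on a site working from 9.1.4.2 without also applying 9.1.3. The documents give no Grade 3 rash rate, so no number of affected patients is claimed. The Table 5 row for repeat appearances is broken in the available text, so nothing is claimed about repeat events.

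A reader might infer that the protocol authorizes dosing through a related Grade 3 rash, or that the primary result is at risk. The documents support neither: the pointers to 9.1.3 and the 9.1.3.1 criteria weigh against the former, and nothing here changes PFS-6, the power or the analysis.

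**What to change.** - **Section 9.1.4.2, hold sentence.** Replace with: *Drug-related Grade 3 rash is managed per Section 9.1.3 and Table 5: interrupt until Grade 1 or lower and, if resumed, resume at 250 mg/day; beyond 21 days, only with Medical Monitor permission.* Grade 3 rash judged unrelated stays under the investigator's discretion at the opening of 9.1.4.
- **Section 9.1.4.2, same-dose sentence.** Limit it to holds for Grade 2 or lower rash, or for rash judged unrelated to study drug.
- **If the sponsor does intend an exception for rash.** List it in the 9.1.3 exceptions, the synopsis list and the Table 5 Grade 3 cell, with its restart dose.
- **Section 9.1.4.1.** Add the same pointer to 9.1.3 for related Grade 3 diarrhea.

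The cost is wording only, with no change to visits, sample size or analysis. Section 16 requires protocol modifications to go to the IRB, with approval before implementation apart from limited exceptions, so the change could wait for the next amendment, with a clarification to sites in the meantime that 9.1.3 governs.
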